9.9. Evaluation of Objectives

The study will be considered successful if we meet both the primary safety and efficacy hypotheses.

9.9.1. Primary Safety Endpoint

The primary safety endpoint of the study is the incidence of Major Adverse Events (MAE), defined as a composite of the following events through one month post-randomization (6 months for new renal artery stenosis):

- All-cause mortality
- End-stage renal disease (ESRD)
- Significant embolic event resulting in end-organ damage
- Renal artery perforation requiring intervention

- Renal artery dissection requiring intervention
- Vascular complications
- Hospitalization for hypertensive crisis not related to confirmed non-adherence with medications or the protocol
- New renal artery stenosis >70%

The primary safety analysis will be performed using the ITT population defined in 9.1.3.1.

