5.1. Primary Endpoints

There are two primary endpoints in this study (one efficacy and one safety). The study will be considered successful if both the primary safety and efficacy endpoint hypotheses are met.

Powered Primary Efficacy Endpoint:

Baseline adjusted change (using analysis of covariance, ANCOVA) in SBP from baseline (screening visit 2, SV2) to 6 months post-procedure as measured by 24-hour ABPM.

Powered Primary Safety Endpoint:

Incidence of Major Adverse Events (MAE), defined as a composite of the following events, through one-month post-randomization (6 months for new renal artery stenosis):

- All-cause mortality
- End-Stage Renal Disease (ESRD)
- Significant embolic event resulting in end-organ damage
- Renal artery perforation requiring intervention
- Renal artery dissection requiring intervention
- Vascular complications
- Hospitalization for hypertensive crisis not related to confirmed non-adherence with medications and/or the protocol
- New renal artery stenosis $> 70\%$, confirmed by angiography and as determined by the angiographic core laboratory

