9.1.3. Analysis Sets

9.1.3.1. Intention-To-Treat (ITT) Population

All randomized subjects analyzed according to their randomized treatment. Subjects who meet the anti-hypertensive medication escape criteria (office SBP ≥ 180 mmHg or < 115 mmHg associated with symptoms of hypotension or safety concern requiring medication changes) will be analyzed using Last Observation Carried Forward (LOCF) for their blood pressure measurements. Safety outcomes, and office and ambulatory blood pressure outcomes at each follow-up visit will be presented for this population.

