9.1.4. Crossover Procedures

Control subjects may crossover to receive renal denervation therapy after completing their 6 month follow-up visit. For the subjects who have already completed their 6-month visit at the time crossover procedures are available per protocol, the decision to crossover must take place at their next in-person visit (6, 12, 24 and 36-month follow-up or Unscheduled visit). All subjects will have 30 days from that visit to undergo the crossover procedure. Subjects that are more than 30 days from 6, 12, 24 or 36-month or unscheduled visit, must complete a crossover baseline visit prior to having the crossover renal denervation procedure. To crossover, the required baseline data must be collected, and the subject cannot meet any of the anatomical or eGFR exclusion criteria. Crossover subjects will undergo follow up visits at 1, 3, 6, 12, 24, and 36 months post-procedure. Subjects who do not meet required eligibility for crossover on the day of the procedure will undergo follow-up visits according to their original follow-up schedule. Crossover procedures will be offered once and will not be available at a later time if it was declined by the control subject during the allowed 30-day window.

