where π is the MAE rate for patients undergoing renal denervation. Under the assumption that the true rate is 3.5%, and using a one-sided 0.05 level of significance, an evaluable sample size of 253 renal denervation patients yields 80% power to reject the null hypothesis in favor of the alternative. The exact binomial test was used for the sample size calculation for the primary safety endpoint hypothesis.

In other words, the primary safety endpoint hypothesis is designed to show whether the true MAE rate is lower than 7.1%. Compared to the literature reported event rates for renal intervention, we believe that these thresholds are appropriate for demonstrating safety of the device given the expected performance rates of similar renal intervention trials, particularly when balanced with the expected blood pressure reductions.

Medtronic proposes multiple sources of study patients as shown in **Table 2** below to ensure 253 patients treated with the Symplicity Spyral catheter (including branch treatment) are available for analysis. The first 253 subjects with evaluable safety data from the sources in Table 2 will be used to perform the primary safety endpoint analysis.

With a sample size of 253 and a one-sided significance level of 0.05, a maximum of 11 subjects with MAE will enable us to meet the safety primary endpoint, resulting in an event rate of 4.3% with a one-sided 95% upper confidence bound of 7.09% using the exact binomial method. The primary safety endpoint analysis will only be performed once using the first 253 subjects as detailed in this section. We will continue to report safety outcomes for all study subjects under secondary safety objectives as outlined in section 9.9.2.

Table 2: Study Sources of Patients for Primary Safety Endpoint Data

Study
SPYRAL HTN-OFF MED prior data (First 80 Subjects) Randomized 1:1 to RDN:CONTROL

⁸ Jaff MR, Bates M, Sullivan T, et al. Significant reduction in systolic blood pressure following renal artery stenting in patients with uncontrolled hypertension: results from the HERCULES trial. *Catheter Cardiovasc Interv.* 2012 Sep 1;80(3):343-50.

⁹ Bersin RM, Ansel G, Rizzo A, et al. Nine-Month Results of the REFORM Study: A Prospective, Single-Arm, Multicenter Clinical Study of the Safety and Effectiveness of the Formula Balloon-Expandable Stent for Treatment of Renal Artery Stenosis. *Catheterization and Cardiovascular Interventions* 82:266–273 (2013).

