SPYRAL PIVOTAL – SPYRAL HTN-OFF MED Randomized 1:1 to RDN:CONTROL
SPYRAL HTN-ON MED First 106 Randomized 1:1 to RDN:CONTROL
SPYRAL HTN ON MED Extension Randomized 2:1 to RDN:CONTROL
SPYRAL HTN-OFF MED Crossovers (from prior and Pivotal)
SPYRAL HTN-ON MED Crossovers (from first 106 and Extension)

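### The primary safety test is in 253 denervated patients including crossovers, but the SAP assigns it an ITT population and a post-randomization clock that do not fit crossovers

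*SAP*

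**What the plan says.** **Population.** Section 9.9.1: "The primary safety analysis will be performed using the ITT population defined in 9.1.3.1". Section 9.1.3.1 defines that population as "All randomized subjects analyzed according to their randomized treatment".

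**Window.** Section 5.1 counts events "through one-month post-randomization (6 months for new renal artery stenosis"). Section 9.9.1 repeats the same anchor: "composite of the following events through one month post-randomization (6 months for new renal artery stenosis").

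**Parameter and sample.** In section 9.9.1.1 the quantity tested "is the MAE rate for patients undergoing renal denervation". Several study sources are pooled "to ensure 253 patients treated with the Symplicity Spyral catheter (including branch treatment) are available for analysis". The first 253 subjects with evaluable safety data are used, the analysis is run once, and at most 11 subjects with an MAE meets the endpoint.

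**Crossovers as a source.** Table 2 has a row for OFF-MED crossovers and one for "SPYRAL HTN-ON MED Crossovers (from first 106 and Extension").

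**When crossover happens.** Section 9.1.4: "Control subjects may crossover to receive renal denervation therapy after completing their 6 month follow-up visit". It then schedules crossover visits at 1, 3, 6, 12, 24 and 36 months after the crossover procedure.

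**The concern.** The population sentence and the window describe a comparison by randomized arm. The hypothesis and Table 2 describe a single group of denervated patients, some of whom were randomized to control and denervated at least about six months later. The SAP never says that the MAE clock restarts at the crossover procedure.

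Sections 5.1 and 9.9 make this one of two hypotheses that must both be met for study success, and it is a single pass/fail count. As written, the programmer has to decide which instruction to override. One available choice, keeping crossovers in the 253 but counting from randomization, would add patients whose observation window covers their sham period and not their denervation. That would dilute the event rate in the direction of passing.

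**Working it through.** **1. The plan's own figures reproduce.** Inputs from section 9.9.1.1: n = 253, null rate 7.1%, assumed true rate 3.5%, one-sided 0.05, exact binomial, pass if X ≤ 11.

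- Type I error: P(X ≤ 11 | 253, 0.071) = 0.0496.
- Power: P(X ≤ 11 | 253, 0.035) = 0.820. The stated figure is 80%; the excess is the usual discreteness of the exact test.
- One-sided 95% Clopper-Pearson upper bound for 11/253 (4.3%) = 7.09%, as stated.
- With 12 events the bound is 7.57% and the type I error 0.085, so 11 is the right limit.

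**2. The three possible readings for an ON-MED crossover.**

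| Reading | Consequence |
|---|---|
| Strict ITT (9.9.1 with 9.1.3.1) | The subject stays in the control arm. The crossover rows of Table 2 contribute nothing, and RDN-randomized subjects who were not treated are kept, although 9.9.1.1 requires treated patients. |
| Counted among the 253, clock from randomization (5.1, 9.9.1) | The one-month window closes about five months before crossover is allowed. No perforation, dissection, embolic or vascular event from the crossover procedure can count. |
| Counted among the 253, clock from own denervation | Agrees with the parameter in 9.9.1.1, but the ITT population and the post-randomization window are then both wrong for this endpoint. |

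For stenosis under the second reading, the 6-month window offers only marginal overlap. Section 9.9.2 gives a lower visit limit of day 166 and counts events to day 180, so a crossover soon after an early visit could have at most about 180 − 166 = 14 days inside it.

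**3. No other rule fills the gap.** The As Treated set (9.1.3.7) covers blood pressure outcomes out to 6 months and reassigns only untreated RDN subjects. The 180- and 166-day limits in 9.9.2 have no stated origin. Chronic safety is timed from the procedure in 5.2 and from randomization in 9.9.2.

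**4. Size under the second reading.** Let m crossovers have sham-period MAE rate q and let the other 253 − m patients have rate 7.1%. Type I error = P(X ≤ 11) with X = Bin(253 − m, 0.071) + Bin(m, q). Both m and q are assumptions.

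| m | q = 0% | q = 1% | q = 2% |
|---|---|---|---|
| 10 | 0.069 | 0.066 | 0.063 |
| 25 | 0.109 | 0.098 | 0.088 |
| 50 | 0.217 | 0.181 | 0.150 |

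**5. Is there room for crossovers?** RDN-arm supply before attrition, from the 1:1 and 2:1 ratios in section 8 and Table 2. The ON-MED first 106 give 53, the OFF-MED prior 80 give 40, and later ON-MED subjects give two thirds. The enrollment totals (260 maximum, 130 at the first look) are taken both as including and as excluding the first 80.

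| Enrollment | ON-MED RDN | Plus OFF-MED prior | Short of 253 |
|---|---|---|---|
| 260 including first 80 | 53 + 154 × 2/3 ≈ 156 | 196 | 57 |
| 260 excluding first 80 | 53 + 234 × 2/3 = 209 | 249 | 4 |
| 130 including first 80 | 53 + 24 × 2/3 = 69 | 109 | 144 |
| 130 excluding first 80 | 53 + 104 × 2/3 ≈ 122 | 162 | 91 |

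The shortfall must come from the OFF-MED pivotal RDN arm, whose size the SAP does not give, or from crossovers. So m could be zero or substantial.

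**The case against.** The strongest reply is that the intent is clear. Section 9.9.1.1 is the specific section: it defines the rate in denervated patients, requires treatment with the study catheter and names both crossover groups. The ITT line is then a stray general sentence, and nobody would read two explicit Table 2 rows as empty. Section 9.1.4 sets new baseline requirements for crossover and schedules 1- and 6-month visits after the procedure, which match the two MAE windows. Section 9.9.2 follows crossovers as their own group to 36 months post-procedure. On that reading the error rate and power are as designed, and the inflation figures describe a choice few analysts would make. For index subjects, randomization and procedure appear nearly to coincide, so the anchor matters only for crossovers. The protocol may also settle the timing.

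Much of this stands. The procedure clock is probably what was meant, and the inflation is not evidence of bias. But a visit schedule does not define an endpoint window, and the SAP states the post-randomization window twice for this endpoint. Following that text literally gives a wrong count for crossovers. A protocol that is clear would not remove the conflict between sections of the SAP itself.

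**Conclusion.** The concern holds. The stated population and window for the primary safety endpoint contradict the single-group test and its Table 2 sources, and time zero for crossovers is missing. It should be fixed before the analysis, because it governs a one-time test that study success depends on.

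The defect lies in the definitions. N = 253, the 11-event limit and the 7.09% bound are correct and remain so when each patient is counted from their own denervation (type I error 0.0496, power 0.82). Only if crossovers are counted from randomization does type I error rise, to between 0.063 and 0.217 over the assumed range of 10 to 50 crossovers and a 0–2% sham-period rate. The SAP gives neither quantity, nor the timing of OFF-MED crossovers, so this shows what depends on the wording and is not an estimate of actual bias.

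**What to change.** - In 9.9.1 and 9.9.1.1, replace ITT for this endpoint with all Table 2 subjects who underwent denervation with the study catheter.
- In 5.1, 9.9.1 and 9.9.1.1, start each subject's MAE window (1 month; 6 months for new stenosis) at that subject's own denervation: the index procedure for RDN-arm subjects, the crossover procedure for crossovers.
- Keep ITT for the RDN-versus-control safety comparisons in 9.9.2, and use one time anchor for chronic safety in 5.2 and 9.9.2.
- While editing, state how the first 253 are ordered across sources, since a crossover's place depends on which date is used.

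The cost is SAP wording, a check that the revised 5.1 definition agrees with the protocol, and one derived time-zero variable. Section 9.1.4 already schedules the 1- and 6-month post-procedure visits for ON-MED crossovers. The sample size and the event limit do not change.

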9.9.1.1. Primary Safety Endpoint Analysis

Medtronic is using a performance goal approach to power the primary safety endpoint.

The safety performance goal for the Major Adverse Event (MAE) rate was developed based on review of and comparison to event rates of other renal interventions. The review of renal intervention literature reported event rates of between 3.6 and 17.2%. The reported events differed among the studies; however, for a subset of these studies, we could estimate rates for a composite of events similar to our protocol's MAE composite (see **Table 1** below). The major adverse event rate from these studies was 7.1%.

Table 1: MAE Rates of Literature Reported Studies

	MAE Rate
ROCHA ¹	4.8%
ASTRAL ²	10.1%
Bax ³	17.2%
Van Jaarsveld ⁴	3.6%
Laird ⁵	8.0%
Coral ⁶	5.1%
Bradaric ⁷	5.7%

¹ Rocha-Singh K, Jaff MR, Rosenfield K, ASPIRE-2 Trial Investigators. Evaluation of the safety and effectiveness of renal artery stenting after unsuccessful balloon angioplasty: the ASPIRE-2 study. J Am Coll Cardiol. 2005 Sep 6;46(5):776-83.

² Wheatley K, Ives N, Gray R, et al. Revascularization versus medical therapy for renal-artery stenosis. N Engl J Med 2009; 361:1953–1962.

³ Bax L, Woittiez AJ, Kouwenberg HJ, et al. Stent placement in patients with atherosclerotic renal artery stenosis and impaired renal function: a randomized trial. Ann Intern Med 2009; 150:840–841.

⁴ Van Jaarsveld, et al. The effect of balloon angioplasty on hypertension in atherosclerotic renal-artery stenosis. N Engl J Med 2000; 342: 1007-14.

⁵ Laird, et al. Safety and efficacy of renal artery stenting following suboptimal renal angioplasty for de novo and restenotic ostial lesions: results from a nonrandomized, prospective multicenter registry. J Vasc Interv Radiol 2010; 21: 627-637.

⁶ Cooper CJ, Murphy TP, Cutlip DE, et al. Stenting and Medical Therapy for Atherosclerotic Renal-Artery Stenosis. NEJM 2014; 370(1): 13-22.

⁷ Bradaric, C. et al. Drug-eluting stents versus bare-metal stents for the prevention of restenosis in patients with renovascular disease.

Jaff ⁸	6.9%
Bersin ⁹	9.8%
Overall Average (weighted by study size)	7.1%

The performance goal is set to be 7.1%, which is the meta-analysis rate from historical trials in **Table 1**.

The primary safety null and alternative hypotheses are:

$$H_0: \pi \geq 7.1\% \text{ vs.}$$

$$H_a: \pi < 7.1\%$$

where π is the MAE rate for patients undergoing renal denervation. Under the assumption that the true rate is 3.5%, and using a one-sided 0.05 level of significance, an evaluable sample size of 253 renal denervation patients yields 80% power to reject the null hypothesis in favor of the alternative. The exact binomial test was used for the sample size calculation for the primary safety endpoint hypothesis.

In other words, the primary safety endpoint hypothesis is designed to show whether the true MAE rate is lower than 7.1%. Compared to the literature reported event rates for renal intervention, we believe that these thresholds are appropriate for demonstrating safety of the device given the expected performance rates of similar renal intervention trials, particularly when balanced with the expected blood pressure reductions.

Medtronic proposes multiple sources of study patients as shown in **Table 2** below to ensure 253 patients treated with the Symplicity Spyral catheter (including branch treatment) are available for analysis. The first 253 subjects with evaluable safety data from the sources in Table 2 will be used to perform the primary safety endpoint analysis.

With a sample size of 253 and a one-sided significance level of 0.05, a maximum of 11 subjects with MAE will enable us to meet the safety primary endpoint, resulting in an event rate of 4.3% with a one-sided 95% upper confidence bound of 7.09% using the exact binomial method. The primary safety endpoint analysis will only be performed once using the first 253 subjects as detailed in this section. We will continue to report safety outcomes for all study subjects under secondary safety objectives as outlined in section 9.9.2.

Table 2: Study Sources of Patients for Primary Safety Endpoint Data

Study
SPYRAL HTN-OFF MED prior data (First 80 Subjects) Randomized 1:1 to RDN:CONTROL

⁸ Jaff MR, Bates M, Sullivan T, et al. Significant reduction in systolic blood pressure following renal artery stenting in patients with uncontrolled hypertension: results from the HERCULES trial. *Catheter Cardiovasc Interv.* 2012 Sep 1;80(3):343-50.

⁹ Bersin RM, Ansel G, Rizzo A, et al. Nine-Month Results of the REFORM Study: A Prospective, Single-Arm, Multicenter Clinical Study of the Safety and Effectiveness of the Formula Balloon-Expandable Stent for Treatment of Renal Artery Stenosis. *Catheterization and Cardiovascular Interventions* 82:266–273 (2013).

SPYRAL PIVOTAL – SPYRAL HTN-OFF MED Randomized 1:1 to RDN:CONTROL
SPYRAL HTN-ON MED First 106 Randomized 1:1 to RDN:CONTROL
SPYRAL HTN ON MED Extension Randomized 2:1 to RDN:CONTROL
SPYRAL HTN-OFF MED Crossovers (from prior and Pivotal)
SPYRAL HTN-ON MED Crossovers (from first 106 and Extension)

9.9.2. Secondary Safety Objectives

The following secondary safety endpoints will be assessed:

- Acute/Procedural Safety Secondary Endpoints – Compared Between Groups at 1 Month Post-Procedure
 - Significant embolic event resulting in end-organ damage
 - Renal artery perforation requiring intervention
 - Renal artery dissection requiring intervention
 - Vascular complications
 - End-stage renal disease (ESRD)
 - $\geq 40\%$ decline in eGFR
 - Increase in serum creatinine $>50\%$ from screening visit 2
 - New myocardial infarction
 - New stroke
 - Renal artery re-intervention
 - Major bleeding according to TIMI definition (i.e. intracranial hemorrhage, $\geq 5\text{g/dl}$ decrease in hemoglobin concentration, a $\geq 15\%$ absolute decrease in hematocrit, or death due to bleeding within 7 days of the procedure)
 - New renal artery stenosis $>70\%$
 - Hospitalization for hypertensive crisis not related to confirmed non-adherence with medication and/or protocol
- Chronic Safety Secondary Endpoints - Compared Between Groups at 3, 6, 12, 24, and 36 months post-randomization.
 - Composite Safety Endpoint, defined as a composite of the following events:
 - All-cause mortality
 - End-stage renal disease (ESRD)
 - Significant embolic event resulting in end-organ damage
 - Renal artery perforation requiring intervention
 - Renal artery dissection requiring intervention
 - Vascular complications
 - Hospitalization for hypertensive crisis not related to confirmed non-adherence with medications and/or the protocol
 - New renal artery stenosis $>70\%$

- $\geq 40\%$ decline in eGFR
- Increase in serum creatinine $>50\%$ from screening visit 2
- New myocardial infarction
- New stroke
- Renal artery re-intervention
- Major bleeding according to TIMI definition (i.e. intracranial hemorrhage, $\geq 5\text{g/dl}$ decrease in hemoglobin concentration, a $\geq 15\%$ absolute decrease in hematocrit, or death due to bleeding within 7 days of the procedure)
- Hospitalization for hypertensive crisis not related to confirmed non-adherence with medication and/or protocol
- Summary of Health-related Quality of Life (HRQoL) analysis based on reporting measures using accepted QoL instruments (EQ5D)

The safety endpoints will be adjudicated by the Clinical Events Committee (CEC). The following algorithm will be used to evaluate the safety event rates: The denominator will include all subjects who either had a CEC adjudicated event prior to the time of interest (180 days for 6 months events, for example), or had last contact date that is beyond the lower window of the follow up (166 days for 6 month events, for example). The numerator will include all subjects who had CEC adjudicated events up to the time of interest (180 days for 6 months events, for example).

The secondary safety endpoints, out to 6-months follow-up, will be compared between RDN and control groups using Fisher's exact test. Two-sided 95% confidence intervals of the difference between treatment groups will also be presented.

After 6-months follow-up, control subjects may crossover (undergo renal denervation), and secondary safety endpoints will be summarized by group (RDN, Crossovers, Non-Crossovers). RDN vs. Crossover vs. Non-Crossover groups will be compared out to 36 months post-procedure using chi-square tests for categorical data and ANOVA for continuous data.

The secondary safety analyses will be performed using the ITT population defined in section 9.1.3.1.

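### The creatinine safety endpoint is measured from screening visit 2 with no exception for crossover subjects, whose denervation comes about six months or more after that visit

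*SAP*

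**What the plan says.** SAP sections 5.2 and 9.9.2 list the creatinine endpoint among both the acute (1-month) and the chronic (3- to 36-month) secondary safety endpoints, each time as "Increase in serum creatinine $>50\%$ from screening visit 2". Neither section gives a separate rule for any group. The companion endpoint, an eGFR decline of at least 40%, appears in the same lists without a reference visit.

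Section 9.1.4 sets the crossover timetable: "Control subjects may crossover to receive renal denervation therapy after completing their 6 month follow-up visit". Controls already past that visit when crossover becomes available decide at their next in-person visit, which may be as late as month 36. A subject more than 30 days from a listed visit "must complete a crossover baseline visit prior to having the crossover renal denervation procedure". The section adds: "To crossover, the required baseline data must be collected, and the subject cannot meet any of the anatomical or eGFR exclusion criteria". Follow-up then restarts: "Crossover subjects will undergo follow up visits at 1, 3, 6, 12, 24, and 36 months post-procedure".

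Section 9.9.2 makes crossovers a group of their own in the safety analysis: "RDN vs. Crossover vs. Non-Crossover groups will be compared out to 36 months post-procedure". No analysis section says what the crossover baseline is used for.

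**The concern.** For a crossover subject the follow-up clock starts at the crossover denervation, but the only written creatinine reference belongs to the original screening. A programmer following the text would compare a value taken one month after denervation with one taken before the subject's whole control period. For a subject in the RDN arm, the same endpoint compares a post-procedure value with one taken before that procedure. The three-group comparison would therefore set two different quantities side by side under one label.

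At stake is the renal safety reading for crossovers, who did receive the device. Kidney change during the control period could be charged to denervation, or could hide a rise after it.

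**Working it through.** The SAP states no event rate, power or sample size for the creatinine or eGFR endpoints, so there is no planned figure to reproduce. The check covers the age of the reference value and the trigger that results.

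**Age of the reference value.** Crossover follows the 6-month visit. Section 9.9.2 gives 166 days as the lower window for 6-month events, and 166 / 30.4375 = 5.5 months. The interval from screening visit 2 to the original procedure comes on top and is not stated, so the shortest gap is about six months. A decision at the 36-month visit makes it about 36 months. Ignoring the unstated interval, the approximate time from screening visit 2 to the measurement is:

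| Measurement | RDN arm | Crossover at month 6 | Crossover at month 36 |
|---|---|---|---|
| 1 month post-procedure | 1 | 6 + 1 = 7 months | 36 + 1 = 37 months |
| 36 months post-procedure | 36 | 6 + 36 = 42 months | 36 + 36 = 72 months |

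**Effect on the trigger.** Let r be creatinine just before the crossover procedure divided by creatinine at screening visit 2. The written rule is met when the later value exceeds 1.5 times the screening value. Measured from the pre-procedure value, that is a rise of more than 1.5/r − 1. The SAP gives no creatinine drift, so the values of r are assumptions:

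| r (assumed) | Rise after crossover that must be exceeded |
|---|---|
| 0.8 | 87.5% |
| 0.9 | 66.7% |
| 1.0 | 50.0% |
| 1.1 | 36.4% |
| 1.2 | 25.0% |
| 1.3 | 15.4% |
| 1.4 | 7.1% |

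With the pre-procedure value as reference, the trigger is 50% for every r.

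**Both directions, with assumed values in any common unit.**
- Counted although the rise after the procedure is small: 1.00 at screening visit 2, 1.30 before crossover, 1.55 after. From screening, 1.55/1.00 = +55%, an event. From the pre-procedure value, 1.55/1.30 = +19%, no event.
- Not counted although the rise after the procedure is large: 1.30 at screening visit 2, 1.00 before crossover, 1.60 after. From screening, 1.60/1.30 = +23%, no event. From the pre-procedure value, 1.60/1.00 = +60%, an event.

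**Reach.** The major adverse event composite in sections 5.1 and 9.9.1 has no creatinine or eGFR threshold. Table 2 counts crossovers as a source for that analysis, but this reference does not enter it. The RDN-versus-control safety comparison runs to 6 months, before any crossover. Only the later comparison of RDN, crossover and non-crossover groups is touched.

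**The case against.** The strongest reply is that the endpoint list is general and says nothing specific about crossovers. Section 9.1.4 requires baseline data before crossover, and the natural purpose of those data is to supply a new reference. The Version History entry for 5.1 says the algorithms for selecting lab values were moved to the study table specifications, which may hold the rule. Section 9.9.2 also sends safety endpoints to the Clinical Events Committee, and the eGFR exclusion at crossover limits how far kidney function can have fallen beforehand.

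Parts of this stand. The sponsor may intend the crossover baseline, and the unseen specifications may use it. But an algorithm for selecting a lab value is not shown to change the reference visit that the endpoint definition itself names. Adjudicating a percentage rise still needs a denominator, and the SAP gives the committee no other. The eGFR exclusion bounds decline on one side only and does not remove drift within the eligible range.

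A reader might also infer that both renal endpoints are tied to screening visit 2. The text does not support that: only creatinine is, and the eGFR reference is simply unstated, which alone would be missing detail. Nor does the SAP show that misclassified events will occur, or how often.

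**Conclusion.** The creatinine definition, taken as written, is wrong for crossover subjects. Its reference predates their denervation by about six months at the least and by about 36 months for the latest crossovers. Their event rate would then combine the control period with the period after the procedure.

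The size per subject depends on drift. Over the assumed range of r from 0.8 to 1.4, the effective trigger runs from 87.5% down to 7.1% instead of 50%. How many subjects this would reclassify cannot be derived from the SAP, because it reports neither creatinine drift nor the number of crossovers.

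The consequence is limited to a non-randomised secondary comparison that decides no hypothesis. It would be an over-reading to conclude that the trial's primary safety result or its 6-month randomised safety comparison is compromised. The point is worth correcting because the section's own follow-up clock and the stated reference do not fit together, and because a baseline chosen after events are seen is hard to defend.

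**What to change.** In sections 5.2 and 9.9.2, add a rule on the reference value:
- For crossover subjects, creatinine events after the crossover procedure use the last value before that procedure. This comes from the qualifying visit if within 30 days, otherwise from the crossover baseline visit. If no creatinine was taken there, use the most recent earlier value.
- Screening visit 2 remains the reference for RDN subjects, for non-crossovers and for control time before crossover.
- The same references apply to the eGFR decline of at least 40%, for all groups.

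The thresholds stay as they are. The cost is SAP wording and one extra derivation rule, best fixed before the crossover safety tables are produced. The fallback is needed because section 9.1.4 does not list creatinine among the required crossover baseline data, so some crossovers may lack a recent value. Reporting how many subjects rely on the fallback would show how much it matters.

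### The SAP's event-rate rule (9.9.2) stops the 6-month numerator at day 180 but takes event-free subjects from day 166, so events first found at a 6-month assessment after day 180 are scored as event-free

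*SAP*

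**What the plan says.** The SAP has one algorithm for turning adjudicated events into rates. It stands in section 9.9.2 (Secondary Safety Objectives) and is introduced in general terms: "The following algorithm will be used to evaluate the safety event rates".

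- **Numerator:** "The numerator will include all subjects who had CEC adjudicated events up to the time of interest (180 days for 6 months events".
- **Denominator, subjects with an event:** those who "had a CEC adjudicated event prior to the time of interest (180 days for 6 months events".
- **Denominator, event-free subjects:** those who "had last contact date that is beyond the lower window of the follow up (166 days for 6 month events".

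The primary safety endpoint (sections 5.1 and 9.9.1) counts MAE "through one month post-randomization (6 months for new renal artery stenosis". Stenosis is thus the only MAE component with a 6-month horizon. Section 5.1 also requires confirmation by angiography and determination by the core laboratory.

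Section 9.9.1.1 tests the MAE rate once, in the first 253 subjects with evaluable safety data, against a 7.1% performance goal. It states that "a maximum of 11 subjects with MAE will enable us to meet the safety primary endpoint". It gives no counting rule and does not define evaluable.

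**The concern.** The two cut-offs are not aligned. Day 166 is called the lower window of the follow-up, so an upper edge exists and some 6-month visits can be expected after day 180. For an event with a clinical onset date, a fixed-day cut does little harm. For an event that becomes known only when someone is assessed (renal artery stenosis, a 40% eGFR decline, a 50% creatinine rise), the date is usually that of the assessment. Such an event, found at a visit after day 180, drops out of the 6-month numerator while its subject stays in the denominator. For stenosis the gap may widen, because angiographic confirmation can follow the first image and the SAP does not say which date the event carries.

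A smaller effect has the same direction. An event-free subject last seen between days 167 and 179 counts as complete to day 180, and nothing in the algorithm requires that a subject scored as free of stenosis was imaged.

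At stake are the 6-month secondary safety rates and, if the rule also governs the primary endpoint, a single test against a fixed goal in which undercounting favours success.

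**Working it through.** **1. The rule applied to one subject.** Suppose the 6-month assessment on day 185 first shows stenosis above 70%, with no earlier event.

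- Denominator: last contact 185 > 166, so the subject is included.
- Numerator: event day 185 > 180, so the event is not counted.
- Result: the subject is scored as event-free at 6 months.

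This needs no assumption about rates, only an event dated after day 180.

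**2. How many visits could fall late.** The lower edge lies 180 − 166 = 14 days before the target. The SAP gives no upper edge. If the window were symmetric (assumption), it would end on day 194. With visits spread evenly over days 166 to 194 (assumption), 14 of 29 days, or 48%, fall after day 180.

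**3. The plan's own figure.** Inputs from 9.9.1.1: N = 253, goal 7.1%, one-sided 5% level, exact binomial.

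| Events | Observed rate | One-sided 95% upper bound | P(X ≤ events) at 7.1% | Result |
|---|---|---|---|---|
| 11 | 4.35% | 7.09% | 0.0496 | pass |
| 12 | 4.74% | 7.57% | 0.085 | fail |

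The SAP's limit of 11 events and its 7.09% bound are reproduced. At that limit, one uncounted stenosis would change the conclusion.

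**4. Effect on the chance of passing.** Let s be the 6-month stenosis rate and f the share of stenoses dated after day 180. Treat stenosis as those subjects' only MAE. With a true MAE rate of 7.1%, the counted rate is 0.071 − s·f, and the chance of passing is P(X ≤ 11) for a binomial with n = 253 and that rate. Example: s = 1%, f = 0.5 gives 0.071 − 0.005 = 0.066 and P = 0.088. All values of s and f are assumptions. The 3.1% row borrows the 12-month rate in 9.9.2.1 as the top of the range.

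| s | Expected uncounted of 253 (f = 0.5) | f = 0.25 | f = 0.5 | f = 0.75 |
|---|---|---|---|---|
| 0 | 0 | 5.0% | 5.0% | 5.0% |
| 0.5% | 0.63 | 5.8% | 6.7% | 7.7% |
| 1% | 1.27 | 6.7% | 8.8% | 11.6% |
| 2% | 2.53 | 8.8% | 15.0% | 23.9% |
| 3.1% | 3.92 | 11.9% | 24.9% | 44.9% |

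**The case against.** **The rule is in the secondary safety section, and 9.9.1 and 9.9.1.1 do not cite it.** This stands in part. Its use for the primary MAE is by default, because its wording is general and no other rule exists. For the 6-month secondary rates it applies without question.

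**The protocol or the adjudication charter may settle the matter.** The upper window edge, the imaging schedule and the dating of a stenosis are not in the SAP. That limits any statement about frequency. It does not alter what the rule does with an event dated after day 180.

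**A cut at day 180 is a literal reading of an endpoint that runs through 6 months.** This is fair, and it is right for events with a clinical onset date. For events found by assessment it sits badly with a denominator built on a visit window.

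**The denominator also has an upward bias.** It keeps every subject with an event before day 180, whatever the follow-up, and drops event-free subjects lost before day 166. This is true and may offset some of the loss, but it does not restore the uncounted events.

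**Stronger readings that the document does not support:**

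- A reader might infer that a fifth of all MAEs could be lost, which would raise the chance of passing to 22.2%. Only stenosis runs to 6 months, and eGFR and creatinine are not MAE components. With half of stenoses dated late, that loss needs a 6-month stenosis rate of 0.20 × 7.1% / 0.5 = 2.8%, close to the 3.1% that 9.9.2.1 expects at 12 months.
- A reader might infer that a late case could surface only after the primary safety conclusion. The SAP does not say so. The 253 come from six sources, and some may have 12-month data by then.
- A reader might infer that subjects without imaging certainly count as stenosis-free in the primary test. That depends on the meaning of evaluable, which 9.9.1.1 leaves open.

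**Conclusion.** The mismatch is real and follows from the text of 9.9.2 alone: an event first found at a 6-month assessment after day 180 is scored as event-free in the 6-month rate. It affects the 6-month secondary safety rates directly and the stenosis component of the primary MAE by default. Taken alone it lowers the rate.

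Its size cannot be fixed from the SAP. With half of stenoses dated after day 180 and 6-month stenosis rates of 0.5%, 1% or 2%, all assumed, the chance of passing at a true MAE rate of 7.1% moves from 5.0% to 6.7%, 8.8% or 15.0%. If stenosis is rarer, the effect is small. That one event separates pass from fail at 11 is a feature of any exact binomial limit and does not by itself show a large bias. The case for change is that the rule errs in the favourable direction and is cheap to correct, not that the primary safety result is shown to be unsound.

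**What to change.** 1. In 9.9.2, for components detected by scheduled assessment (renal artery stenosis, eGFR decline, creatinine rise), count events found at the visit up to the upper edge of that visit's protocol window. Keep the fixed-day cut for events with a clinical onset date.
2. Date a stenosis to the imaging that prompted its angiographic confirmation.
3. State in 9.9.1.1 that this rule governs the stenosis component of the primary MAE.
4. Keep the primary denominator of 253 as planned. Report how many of those subjects had no renal imaging on or after the lower window edge, and add a sensitivity analysis for them. Removing them would not suit a composite tested once on a fixed N.

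**Cost:** a few sentences in the SAP and a small programming change. The reported 6-month rate may be slightly higher.
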